16.5 EFFICACY ANALYSIS

The efficacy analysis will be performed for both FAS and PP populations. Descriptive statistics and inferential statistics will be performed through intergroup analysis (ANCOVA covariance analysis)-comparing each treatment group (patients treated with HEMAX PFS versus those treated with EPREX/ERYPO®) and an additional intragroup analysis analyzing the variations in hemoglobin (increase from baseline to the average of the visits between weeks 8 and 12) adjusted for the baseline value, using a significance level of 5%. Statistical analysis will be performed with SPSS software or equivalent.

The following parameters will be evaluated for treatment efficacy, according to the objectives defined by the protocol.

The **primary efficacy assessment** will be carried out through the levels of hemoglobin increase from baseline value to the mean value of the visits between week 8 and 12, comparing patients treated with HEMAX PFS versus those treated with EPREX/ERYPO®.

Additionally, **treatment equivalence** will be established if the difference between the two groups excludes a difference between treatment groups greater than 1g/ dl in hemoglobin increase from baseline value to the mean value of the visits between week 8 and 12 with a difference in the mean dose of epoetin alfa in these visits no greater than 20%.

The **secondary efficacy assessment** will be carried out through the evaluation of the following objectives:

- Percentage of responder patients (increase of Hb \geq 1g/ dl) after 12 weeks of treatment, comparing patients treated with HEMAX PFS versus those treated with EPREX/ERYPO®.

- Percentage of transfusion requirement after 12 weeks of treatment, comparing patients treated with HEMAX PFS versus those treated with EPREX/ ERYPO®.
- Intragroup efficacy (HEMAX PFS and EPREX/ ERYPO®) of treatment with Epoetin Alfa through increased levels of hemoglobin from baseline in each one of the intermediate visits until the week 12 visit.
- Evaluate the intragroup efficacy (HEMAX PFS and EPREX/ ERYPO®) of the change from the twice - a - week dosing during the titration phase to a weekly dosing during the maintenance phase through the variation of the hemoglobin levels from week 12 to the weeks 16, 20 and 24.

For **missing hemoglobin data**, the last observation carried forward method will be used.

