3.2.4 Statistical Hypotheses

Treatment equivalence will be established if the difference between the two groups excludes a difference between treatment groups greater than 1g/ dl in hemoglobin increase from baseline value to the mean value of the visits between week 8 and 12 with a difference in the mean dose of epoetin alfa in these visits no greater than 20%.

The following equivalence statistical hypotheses is to be tested at a two-sided significance level of 5%:

- H0: Treatment difference in mean Hb during the primary efficacy evaluation period, between treatment arms (HEMAX PFS versus EPREX/ERYPO®), is within ± 1.0 g/dL or less.
- H1: Treatment difference in mean Hb during the primary efficacy evaluation period, between treatment arms (HEMAX PFS versus EPREX/ERYPO®), is greater than ± 1.0 g/dL.

Only when the primary endpoint achieves equivalence, statistical testing will progress to the secondary endpoints according to the stepdown procedure.

4 Study Methods

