8.1 Primary Efficacy Analysis

The primary efficacy analysis will be performed for Per Protocol population.

The primary efficacy assessment will be carried out through the levels of hemoglobin increase from baseline value to the mean value of the visits between week 8 and 12, comparing patients treated with HEMAX PFS versus those treated with EPREX/ ERYPO®.

Additionally, treatment equivalence will be established if the difference between the two groups excludes a difference between treatment groups greater than 1g/ dl in hemoglobin increase from baseline value to the mean value of the visits between week 8 and 12 with a difference in the mean dose of epoetin alfa in these visits no greater than 20%.

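### SAP 3.2.4 states the equivalence hypotheses the wrong way round, and no confidence interval rule or pair of one-sided tests turns the exclusion rule into a test

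*SAP*

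**What the plan says.** SAP 3.2.4 (Statistical Hypotheses) opens with a decision rule: "Treatment equivalence will be established if the difference between the two groups excludes a difference between treatment groups greater than 1g/ dl", measured on the hemoglobin increase from baseline to the mean of the week 8 to 12 visits. It then says "The following equivalence statistical hypotheses is to be tested at a two-sided significance level of 5"% and prints this pair:

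- "H0: Treatment difference in mean Hb during the primary efficacy evaluation period, between treatment arms (HEMAX PFS versus EPREX/ERYPO®), is within ± 1.0 g/dL" (the line ends with two more words that do not change its sense)
- "H1: Treatment difference in mean Hb during the primary efficacy evaluation period, between treatment arms (HEMAX PFS versus EPREX/ERYPO®), is greater than ± 1.0 g/dL"

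The section closes with a gate: "Only when the primary endpoint achieves equivalence, statistical testing will progress to the secondary endpoints according to the stepdown procedure".

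SAP 8.1 repeats the decision rule ("treatment equivalence will be established if the difference between the two groups excludes a difference between treatment groups greater than 1g/ dl") and attaches a second condition, "with a difference in the mean dose of epoetin alfa in these visits no greater than 20"%. Protocol 16.5 has the same rule ("established if the difference between the two groups excludes a difference between treatment groups greater than 1g/ dl"), as does the Protocol synopsis. The sample size statements in Protocol 16.1 and SAP 5 also speak of ruling out a difference above 1 g/dL.

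For the between-arm comparison of hemoglobin, Protocol 16.5 names ANCOVA. SAP 7 and SAP 8 name ANCOVA or an independent-samples t-test at the 5% level.

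**The concern.** An equivalence claim is made by rejecting a null of non-equivalence. The printed pair does the reverse: equivalence is assumed, and the only thing a significant result could establish is a difference larger than the margin. That contradicts the decision rule printed just above it.

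Swapping the two lines does not finish the job. An ordinary ANCOVA or t-test at 5% tests a difference of zero, which is not the exclusion rule. The stated two-sided 5% level is not tied to an interval. It reads most naturally as a 95% interval, but two one-sided tests at 5% each (a 90% interval) are not excluded. A smaller slip is that the hypotheses refer to mean hemoglobin, while the endpoint is the increase from baseline.

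The primary conclusion and access to secondary testing both hang on this test. The trial is open-label, and SAP 5 reports that an interim analysis gave the expected results and that recruitment ended at 43 of 120 patients. Fixing the level or the model only after that point leaves room for a choice that depends on the data.

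**Working it through.** **Direction.** Set side by side:

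| Place | What must be shown to claim equivalence |
|---|---|
| SAP 3.2.4, decision rule | a difference above 1 g/dL is excluded |
| SAP 8.1, Protocol 16.5, Protocol synopsis | the same |
| Protocol 16.1, SAP 5 | a difference above 1 g/dL is ruled out |
| SAP 3.2.4, printed H0 and H1 | nothing: equivalence is the null, so rejection shows non-equivalence |

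Every statement except the printed pair needs non-equivalence as the null.

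**Inputs.** Margin 1.0 g/dL (SAP 3.2.4); planned 60 per arm and 80% power (SAP 5); enrolled 23 and 20 (SAP 5). Neither document gives an SD, an assumed true difference or a dropout rate. The planned 120 therefore cannot be reproduced, and every SD below is an assumed residual SD. The model is a two-sample t with 23 + 20 − 2 = 41 degrees of freedom; ANCOVA with one covariate would have 40. The Per Protocol set can only be the enrolled size or smaller.

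**Interval half-width.** t × SD × √(1/23 + 1/20), where the root is 0.3057 and t is 2.020 (95%) or 1.683 (90%).

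- SD 1.0: 2.020 × 1.0 × 0.3057 = 0.62 g/dL (95%); 1.683 × 1.0 × 0.3057 = 0.51 g/dL (90%).
- SD 1.5: 0.93 and 0.77 g/dL.
- The half-width reaches the margin at SD 1.62 (95%) or 1.94 (90%). Beyond that, equivalence can be shown only if the sample SD falls below the true one.

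**Chance that the interval lies wholly within ±1.0.** With SE = SD × 0.3057, sample standard error se and true difference d, the probability given se is Φ((1 − d − t·se)/SE) − Φ((−1 − d + t·se)/SE), or zero if that is negative. It is then averaged over the chi-square distribution of the sample variance. An interval that passes at 95% also passes at 90%, so the last column is a simple subtraction. At 23 and 20, with d = 0:

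| Assumed SD | 95% interval | 90% interval | 90% passes, 95% fails |
|---|---|---|---|
| 0.8 | 95.8% | 98.2% | 2.5% |
| 1.0 | 78.2% | 88.4% | 10.1% |
| 1.5 | 15.7% | 38.3% | 22.6% |
| 1.68 | 4.8% | 21.8% | 16.9% |
| 1.87 | 1.0% | 9.4% | 8.4% |

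Differences are taken before rounding. With d = 1.0 the rule passes at most 2.5% of the time (95%) or 5% (90%).

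**Tied to the planned power.** The SD that gives 80% power at 60 per arm with d = 0 is 1.676 (95%) or 1.861 (90%). At those SDs, power with 23 and 20 is 5.0% and 9.8%.

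**Two possible misreadings, neither of them stated in the plan.**

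- If failure to reject the printed null at 2.5% per side were taken as equivalence, a true difference of 1.0 g/dL would pass 97.5% of the time across SDs 1.0 to 1.87. A true 1.25 would pass 88%, 92% and 94% of the time at SD 1.0, 1.5 and 1.87. With 60 per arm those figures are 73%, 85% and 89%, so the smaller trial would pass more easily.
- If a non-significant t-test at 5% were taken as equivalence, a true 1.0 at 23 and 20 would pass 11%, 43% and 60% of the time at the same SDs.

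**The case against.** The strongest reply is that the reversal changes nothing if the written decision rule is followed. That rule sits directly above the hypotheses, and a two-sided 5% level combined with excluding a difference above 1 g/dL already amounts to a 95% interval within ±1.0. Much of this stands. The intent is recoverable, 95% is the natural reading, and nowhere do the documents say that non-rejection establishes equivalence. But no interval is written down, and the tests that are named do not carry out the rule.

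The effect of the unstated level also depends on the SD. Entry hemoglobin is confined to between 7.5 and 10.5 g/dL, dosing is interrupted at 11.5 g/dL, and the endpoint averages several visits, so an SD below 1.0 is possible. At SD 0.8 the two readings disagree only 2.5% of the time. That narrows the practical effect but does not remove the defect.

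The low power at the larger SDs comes from enrolling 43 rather than 120, whatever the hypotheses say. It is given here as what a corrected test would face, not as harm done by the wording.

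Finally, the 20% dose condition has no interval or test either, and Protocol 16.5 analyses both FAS and Per Protocol populations while SAP 8.1 uses only the latter. Both are fair points, and the change proposed here settles neither.

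**Conclusion.** The concern holds, with high confidence, and must be fixed before the primary result is reported. The printed hypotheses cannot support an equivalence claim, and the rule that could support one has not been turned into a calculation. With 23 and 20 patients and no true difference, the choice between a 95% and a 90% interval changes the verdict with probability 10% at SD 1.0 and 23% at SD 1.5, falling to 2.5% at SD 0.8. These sizes rest on assumed SDs and a two-sample t model. The reversal and the missing test rule rest on the text alone.

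**What to change.** In SAP 3.2.4 and 8.1, replace the hypotheses and decision rule with wording to this effect:

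> H0: difference ≤ −1.0 or ≥ +1.0 g/dL. H1: −1.0 < difference < +1.0 g/dL. The difference is the between-arm difference in hemoglobin increase from baseline to the mean of the week 8–12 visits. The hemoglobin condition is met only when the two-sided 95% confidence interval for this difference, from an ANCOVA adjusted for baseline hemoglobin, lies entirely within (−1.0, +1.0). Equivalence is concluded only if this condition and the existing 20% condition on mean epoetin alfa dose are both met. Secondary testing proceeds only then. A non-significant ANCOVA or t-test is not evidence of equivalence.

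Two elements are choices and should be labelled as such:

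- **The 95% level.** If two one-sided tests at 5% each were intended, the sponsor should say so and justify it.
- **Baseline-adjusted ANCOVA as the single primary model.** The SAP also allows a t-test and names no covariate for the between-arm ANCOVA.

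Date the change, and disclose that it was made after the interim look and the early end of recruitment.

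The cost is SAP wording and a dated disclosure; no new data are needed. The sponsor's margin, endpoint, dose condition and gate are kept. The price is that, unless the SD is well below 1.5 g/dL, the trial will probably have to be reported as inconclusive on equivalence.

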7.6 Treatment Compliance

The patients should return to the center all the containers with the drug product used during the study, and all the medications that they had not used during the study. The staff in the center recorded in the source document and on the patient accountability individual record, the patient number, and the number of returned containers.

During the study, the monitor checked continuously all the containers with the study medication (used, and non-used containers), and the corresponding accountability forms. At the same time, at each visit the card in which the patient recorded the date and drug product dose administered, is checked. Accountability records of the drug products used during the study were kept in the centers all the time. At the moment the study was ended a final accountability was carried out and all the remnant medication was withdrawn for destruction, as stated in current regulations. .

The following measures will de obtained related to treatment compliance:

- Epoetin dose (IU) administered every week in each group (mean \pm SD): Mean for cumulative doses per patient at the titration stage, maintenance stage, and during the whole treatment
- Number of patients that suspended the treatment at each visit

8 Efficacy Analyses

All efficacy variables will be listed by subject within study site. Data will be summarized by treatment group. Number and percentage will summarize categorical efficacy variables and Number, Mean, Standard Deviation, Minimum and Maximum will summarize continuous efficacy variables, whereas.

Inferential statistics will be performed through intergroup analysis analysis using ANCOVA covariance analysis comparing each treatment group (patients treated with HEMAX PFS versus those treated with EPREX/ ERYPO®) or the statistical “t” Student test for independent samples considering 5% significance level.

An additional intragroup analysis evaluating the variations in hemoglobin (increase from baseline to the average of the visits between weeks 8 and 12) adjusted for the baseline value, using a significance level of 5% will be performed

The assumptions regarding normality and homogeneity will be checked.

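### SAP 3.2.4 writes H0 and H1 on mean Hb level but the equivalence rule on Hb increase, and the analysis text does not name the baseline adjustment that would make the two agree

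*SAP*

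**What the plan says.** SAP 3.2.4 opens with the rule: equivalence holds if the data exclude a between-arm difference "greater than 1g/ dl in hemoglobin increase from baseline value to the mean value of the visits between week 8 and 12", together with a limit of 20% on the difference in mean dose. The hypotheses that follow concern a different quantity, "Treatment difference in mean Hb during the primary efficacy evaluation period", and ask whether it "is within ± 1.0 g/dL or less". Neither hypothesis mentions baseline, increase or change.

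Every other statement of the primary comparison uses the increase: Protocol 6.1, 16.1 and 16.5, and SAP 3.2.2, 3.2.3, 5 and 8.1. SAP 8.1, for example, bases the primary assessment on "levels of hemoglobin increase from baseline value to the mean value of the visits between week 8 and 12".

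On method, SAP 7 and the opening of SAP 8 provide for a between-group analysis "using ANCOVA covariance analysis comparing each treatment group" or, as an alternative, the "Student test for independent samples considering 5% significance level". No rule for choosing is given. Adjustment for baseline appears in the next sentence, which describes a separate within-group analysis. No covariate is named for the between-group ANCOVA.

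**The concern.** The issue is which variable is tested. Whether H0 and H1 point the right way is a separate matter, and swapping them would leave this mismatch in place.

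A comparison of week 8–12 levels and a comparison of increases give the same treatment difference when baseline Hb is in the model. In an unadjusted t-test they do not. As written, the SAP leaves room for either variable with or without adjustment, so the Hb part of the equivalence verdict can depend on which combination is used.

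Three features raise the stakes. Randomisation is stratified by sex and blocked by centre (SAP 4.3), so nothing forces balance on baseline Hb. Under SAP 3.2.4 the primary result decides whether secondary endpoints are tested at all. The trial is open-label, and SAP 5 reports that interim results had been seen when recruitment was stopped at 43 patients.

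**Working it through.** **The plan's own figure.** SAP 5 and Protocol 16.1 claim 80% power at 60 per arm against 1 g/dl. No SD or assumed true difference is given, so the figure can only be solved backwards. With a true difference of 0, margin 1.0 and SE = SD × √(2/60) = 0.1826 × SD:

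- Two one-sided tests, 95% CI: 1/SE = 1.960 + 1.282 = 3.242, so SD = 1.69.
- Two one-sided tests, 90% CI: 1/SE = 1.645 + 1.282 = 2.927, so SD = 1.87.
- One-sided non-inferiority at 0.025: 1/SE = 1.960 + 0.842 = 2.802, so SD = 1.955.
- One-sided at 0.05: 1/SE = 1.645 + 0.842 = 2.487, so SD = 2.20.

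**Identity.** Write B for baseline Hb and Y for the week 8–12 mean. The difference in increase is (Ȳ₁ − B̄₁) − (Ȳ₂ − B̄₂), which equals the difference in level minus the baseline difference (B̄₁ − B̄₂). If B is a covariate, replacing Y by Y − B lowers the coefficient of B by 1 and leaves the treatment coefficient and its SE unchanged.

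**Size of the chance baseline difference.** At 23 v 20, √(1/23 + 1/20) = 0.3057. Baseline SD is assumed. Eligibility confines Hb to 7.5–10.5 g/dl, and a uniform spread over that range has SD 3/√12 = 0.87.

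| Baseline SD | SE of baseline difference | ±1.96 SE |
|---|---|---|
| 0.60 | 0.18 | ±0.36 |
| 0.70 | 0.21 | ±0.42 |
| 0.87 | 0.27 | ±0.52 |

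**Opposite verdicts, by example.** Assume baseline SD 0.75, week 8–12 SD 1.0 and correlation 0.5. Change SD is √(0.5625 + 1 − 0.75) = 0.90. The two-sided 5% level is read as a 95% CI. With t(41) = 2.02, the half-widths are 2.02 × 1.0 × 0.3057 = 0.62 for level and 2.02 × 0.90 × 0.3057 = 0.56 for increase.

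- Level difference 0.30 gives −0.32 to 0.92, a pass. With a baseline difference of −0.30 (about 1.3 SE), the increase difference is 0.60, giving 0.04 to 1.16, a fail.
- Level difference 0.45 gives −0.17 to 1.07, a fail. With a baseline difference of +0.25, the increase difference is 0.20, giving −0.36 to 0.76, a pass.

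**How often.** Normal data were simulated with baseline SD 0.7 or 0.87, baseline-to-change correlation −0.3 or −0.4, and true difference 0 or 0.3 (20,000 trials per setting). The unadjusted 95% CI was compared with ±1.0 for each variable. The 20% dose condition was not modelled.

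| Change SD (assumed) | Verdicts disagree, 23 v 20 | Verdicts disagree, 60 v 60 |
|---|---|---|
| 0.8–1.2 | about 7–35% | about 0–13% |
| 1.7–2.0 | about 1–11% | about 12–22% |

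A second set of simulations used baseline SD 0.6–0.75, week 8–12 SD 1.0–1.2 and correlation 0.3–0.7. At 23 v 20 it gave 17–34% disagreement for true differences of 0–0.5. At 60 v 60 it gave 0–1% at a true difference of 0, 3–10% at 0.3 and 16–21% at 0.5. With baseline Hb as covariate, disagreement was 0% in every setting.

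**Error if the passing variable is reported.** At a true difference of exactly 1.0, 23 v 20, and the example's SDs and correlation, level passes in 2.5% of trials, increase in 2.6%, and they disagree in 3.4%. At least one passes in (2.5 + 2.6 + 3.4)/2 = 4.25%, against a nominal 2.5%.

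**The case against.** The strongest reply is that only one primary variable is really specified. The increase appears in the objectives, the endpoint list, the sample size, SAP 8.1 and the rule directly above the hypotheses. The hypotheses refer to the same period and use the same 1.0 margin, so they read as a careless restatement. No section prescribes a primary test of Hb level, and under randomisation both contrasts have the same expected value. This stands. A reader might infer that the plan has two rival primary endpoints left open on purpose; the documents do not support that.

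A second reply is that the consequence runs through the t-test option and not through the wording of the hypotheses. ANCOVA is the only between-group test in Protocol 16.5, it comes first in SAP 7 and 8, and baseline is the only adjustment variable named anywhere. This also largely stands. With a baseline-adjusted ANCOVA fixed as the primary test, the mismatch would change no verdict. But the SAP attaches the adjustment to the within-group analysis and leaves the t-test available, so the condition is not met.

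A third is that the disagreement rates rest on assumed SDs. That is right. A reader might infer that the problem is serious at 43 patients and negligible at 120. This holds for SDs of 0.8–1.2 with a small true difference. It reverses at 1.7–2.0, near the SD implied by the plan's own sample size. There the 95% half-width at 23 v 20 is already above 1.0 (1.04 at SD 1.69), so both versions usually fail.

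Finally, a reader might infer that the wording was chosen after seeing the data. SAP 5 shows that interim results were known. Nothing shows that level and increase were compared, or that either choice was driven by results.

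**Conclusion.** The mismatch is certain from the text: the rule and the hypotheses in SAP 3.2.4 name different quantities. It has consequences because SAP 7 and 8 permit an unadjusted comparison and do not name baseline Hb as covariate for the adjusted one. That opposite verdicts are possible follows from arithmetic and needs no assumption about the SD.

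The frequency is uncertain. Across the assumed settings with true difference 0–0.3 it runs from about 1% to 35% at 23 v 20 and from 0% to 22% at 60 v 60. These figures cover only the Hb part of the equivalence rule. They also take all 43 enrolled patients, although the primary analysis uses the per-protocol set (SAP 8.1), which requires the week 12 visit and may be smaller.

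Should-fix: the intended variable is clear from the rest of the plan, but the formal test should not depend on the reader inferring it.

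**What to change.** Three edits, which need to be made together:

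1. SAP 3.2.4: write H0 and H1 on the between-arm difference in Hb increase from baseline to the mean of the week 8–12 visits.
2. SAP 8.1: state that the confidence interval used for the equivalence decision comes from an ANCOVA with baseline Hb as covariate.
3. SAP 7 and 8: remove the t-test option for the primary comparison, or label it a sensitivity analysis.

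Editing SAP 3.2.4 alone would leave the unadjusted option in SAP 7 and 8. The cost is a few sentences, with no new data or patients. Because interim results are already known, the change should be dated and its reason recorded.
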